Complete Response (CR): Disappearance of all clinical and radiological evidence of tumor (both *target* and *non-target*). Any pathological lymph nodes (whether target or non-target) must have a reduction in short axis to < 10mm.

Partial Response (PR): At least a 30% decrease in the sum of diameters of target lesions taking as reference the baseline sum, no unequivocal progression of existing non-target lesions and no appearance of new lesions.

Stable Disease (SD): Steady state of disease. Neither sufficient shrinkage to qualify for PR nor sufficient increase to qualify for PD, no unequivocal progression of existing non-target lesions and no appearance of new lesions.

Progressive Disease (PD): At least a 20% increase in the sum of diameters of target lesions taking as reference the smallest sum on study (this includes the baseline sum if that is the smallest on study). In addition to the relative increase of 20%, the sum must also demonstrate

Page 115 of 141

an absolute increase of at least 5mm. Unequivocal progression of existing non-target lesions or the appearance of one or more new lesions will also constitute progressive disease. (Note: the appearance of one or more new lesions is also considered progression). Ascites or pleural effusion will be recorded as disease progression only if proven malignant.

Lymph nodes identified as target lesions should always have the actual short axis measurement recorded (measured in the same anatomical plane as the baseline examination), even if the nodes regress to below 10 mm on study. This means that when lymph nodes are included as target lesions, the 'sum' of lesions may not be zero even if complete response criteria are met, since a normal lymph node is defined as having a short axis of <10mm.

To achieve unequivocal progression in participants with measurable disease on the basis of the non-target disease, there must be an overall level of substantial worsening in non-target disease such that, even in presence of SD or PR in target disease, the overall tumor burden has increased sufficiently to merit withdrawal of study intervention. A modest 'increase' in the size of one or more non-target lesions is usually not sufficient to qualify for unequivocal.

In the absence of measurable disease, the same general concepts apply here as noted above.

Response duration

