using iRECIST for participant management (see Table 10–11 and Figure 10–1). This decision by the investigator should be based on the participant's overall clinical condition.

Clinical stability is defined as the following:

- Absence of symptoms and signs indicating clinically significant progression of disease
- No decline in ECOG performance status
- No requirements for intensified management, including increased analgesia, radiation, or other palliative care

Any participant deemed **clinically unstable** should be discontinued from study intervention at site-assessed first radiologic evidence of PD, and is not required to have repeat tumor imaging for confirmation of PD by iRECIST.

If the investigator decides to continue treatment, the participant may continue to receive study intervention and the tumor assessment should be repeated 4 to 8 weeks later to confirm PD by iRECIST, per investigator assessment.

Tumor flare may manifest as any factor causing radiographic progression per RECIST 1.1, including:

- Increase in the sum of diameters of target lesion(s) identified at baseline to ≥20% and ≥5 mm from nadir
- Note: the iRECIST publication uses the terminology "sum of measurements", but "sum of diameters" will be used in this protocol, consistent with the original RECIST 1.1 terminology
- Unequivocal progression of non-target lesion(s) identified at baseline
- Development of new lesion(s)

iRECIST defines new response categories, including iUPD (unconfirmed progressive disease) and iCPD (confirmed progressive disease). For purposes of iRECIST assessment, the first visit showing progression according to RECIST 1.1 will be assigned a visit (overall) response of iUPD, regardless of which factors caused the progression.

At this visit, target and non-target lesions identified at baseline by RECIST 1.1 will be assessed as usual.

New lesions will be classified as measurable or non-measurable, using the same size thresholds and rules as for baseline lesion assessment in RECIST 1.1. From measurable new lesions, up to 5 lesions total (up to 2 per organ), may be selected as New Lesions – Target. The sum of diameters of these lesions will be calculated, and kept distinct from the sum of diameters for target lesions at baseline. All other new lesions will be followed qualitatively as New Lesions – Non-target.

Assessment at the Confirmatory Imaging

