On the confirmatory imaging, the participant will be classified as progression confirmed (with an overall response of iCPD), or as showing persistent unconfirmed progression (with an overall response of iUPD), or as showing disease stability or response (iSD/iPR/iCR).

Confirmation of Progression

Progression is considered confirmed, and the overall response will be iCPD, if ANY of the following occurs:

Page 125 of 141

- Any of the factors that were the basis for the initial iUPD show worsening
- For target lesions, worsening is a further increase in the sum of diameters of ≥5 mm, compared to any prior iUPD time point
- For non-target lesions, worsening is any significant growth in lesions overall, compared to a prior iUPD time point; this does not have to meet the "unequivocal" standard of RECIST 1.1

For new lesions, worsening is any of these:

- An increase in the new lesion sum of diameters by ≥5 mm from a prior iUPD time point
- Visible growth of new non-target lesions
- The appearance of additional new lesions

Any new factor appears that would have triggered PD by RECIST 1.1

Persistent iUPD

Progression is considered not confirmed, and the overall response remains iUPD, if:

- None of the progression-confirming factors identified above occurs AND
- The target lesion sum of diameters (initial target lesions) remains above the initial PD threshold (by RECIST 1.1)

Additional imaging for confirmation should be scheduled 4 to 8 weeks from the imaging on which iUPD is seen. This may correspond to the next visit in the original visit schedule. The assessment of the subsequent confirmation imaging proceeds in an identical manner, with possible outcomes of iCPD, iUPD, and iSD/iPR/iCR.

Resolution of iUPD

Progression is considered not confirmed, and the overall response becomes iSD/iPR/iCR, if:

- None of the progression-confirming factors identified above occurs, AND
- The target lesion sum of diameters (initial target lesions) is not above the initial PD threshold.

The response is classified as iSD or iPR (depending on the sum of diameters of the target lesions), or iCR if all lesions resolve.

In this case, the initial iUPD is considered to be pseudo-progression, and the level of suspicion for progression is "reset". This means that the next visit that shows radiographic progression, whenever it occurs, is again classified as iUPD by iRECIST, and the confirmation process is repeated before a response of iCPD can be assigned.

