Management Following the Confirmatory Imaging

If repeat imaging does not confirm PD per iRECIST, as assessed by the investigator, and the participant continues to be clinically stable, study intervention may continue and follow the regular imaging schedule. If PD is confirmed, participants will be discontinued from study intervention.

NOTE: If a participant has iCPD as defined above, but the participant is achieving a clinically meaningful benefit, an exception to continue study intervention may be considered following consultation with the sponsor. In this case, if study intervention is continued, tumor imaging

Page 126 of 141

should continue to be performed following the intervals as outlined in this protocol (see Section 1.3.1)

Detection of Progression at Visits after Pseudo-progression Resolves

After resolution of pseudo-progression (i.e., achievement of iSD/iPR/iCR), iUPD is indicated by any of the following events:

Target lesions

• Sum of diameters reaches the PD threshold ($\geq 20\%$ and ≥ 5 mm increase from nadir) either for the first time, or after resolution of previous pseudo-progression. The nadir is always the smallest sum of diameters seen during the entire trial, either before or after an instance of pseudo-progression.

Non-target lesions

- If non-target lesions have never shown unequivocal progression, their doing so for the first time results in iUPD.
- If non-target lesions have shown previous unequivocal progression, and this progression has not resolved, iUPD results from any significant further growth of non-target lesions, taken as a whole.

New lesions

- New lesions appear for the first time
- Additional new lesions appear
- Previously identified new target lesions show an increase of ≥ 5 mm in the new lesion sum of diameters, from the nadir value of that sum
- Previously identified non-target lesions show any significant growth

If any of the events above occur, the overall response for that visit is iUPD, and the iUPD evaluation process (see Assessment at the Confirmatory Imaging above) is repeated. Progression must be confirmed before iCPD can occur.

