The decision process is identical to the iUPD confirmation process for the initial PD, with one exception: if new lesions occurred at a prior instance of iUPD, and at the confirmatory imaging the burden of new lesions has increased from its smallest value (for new target lesions, the sum of diameters is ≥5 mm increased from its nadir), then iUPD cannot resolve to iSD or iPR. It will remain iUPD until either a decrease in the new lesion burden allows resolution to iSD or iPR, or until a confirmatory factor causes iCPD.

Additional details about iRECIST are provided in the iRECIST publication (Seymour et al. 2017).

Page 127 of 141

[figure not shown]
Table 10-11: Imaging and Treatment after First Radiologic Evidence of PD

	Clinica	lly Stable	Clinical	ly Unstable
	Imaging	Treatment	Imaging	Treatment
1st radiologic evidence of PD by RECIST 1.1	Repeat imaging at 4 to 8 weeks at site to confirm PD	May continue study intervention at the local site investigator's discretion while awaiting confirmatory tumor imaging by site by iRECIST.	Repeat imaging at 4 to 8 weeks to confirm PD per physician discretion only	Discontinue study intervention
Repeat tumor imaging confirms PD (iCPD) by iRECIST at the local site	No additional imaging required	Discontinue study intervention (exception is possible upon consultation with sponsor)	No additional imaging required	N/A
Repeat tumor imaging shows iUPD by iRECIST per investigator assessment	Repeat imaging at 4 to 8 weeks to confirm PD. May occur at next regularly scheduled imaging visit.	Continue study intervention at the investigator's discretion.	Repeat imaging at 4 to 8 weeks to confirm PD per investigator's discretion only.	Discontinue study intervention
Repeat tumor imaging shows iSD, iPR, or iCR by iRECIST per investigator assessment.	Continue regularly scheduled imaging assessments	Continue study intervention at the local site investigator's discretion	Continue regularly scheduled imaging assessments	May restart study intervention if condition has improved and/or clinically stable per investigator's discretion. The next tumor image should occur according to the schedule outlined in the SoA (Section 1.3.1).

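### Under the protocol's iRECIST rules, an unconfirmed progression caused only by a new lesion or by non-target disease becomes iSD or iPR on an unchanged repeat scan, so exploratory iRECIST ORR and DOR can count a participant whose triggering lesion never regressed

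*Protocol*

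**What the plan says.** Protocol Section 10.5.3 sets out the sequence.

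- **First progression.** On entering iUPD: "the first visit showing progression according to RECIST 1.1 will be assigned a visit (overall) response of iUPD, regardless of which factors caused the progression". The triggers are growth of the target sum, unequivocal non-target progression, and new lesions.
- **Shared condition at the repeat scan.** Persistence and resolution both begin with "None of the progression-confirming factors identified above occurs AND". The confirming factors cover every lesion type: a further target-sum increase of 5 mm or more, significant non-target growth, a new-lesion sum up by 5 mm or more, visible growth of new non-target lesions, additional new lesions, or any fresh RECIST 1.1 trigger.
- **Persistent iUPD, second condition.** "The target lesion sum of diameters (initial target lesions) remains above the initial PD threshold (by RECIST 1.1".
- **Resolution of iUPD, second condition.** "The target lesion sum of diameters (initial target lesions) is not above the initial PD threshold".
- **Category after resolution.** "The response is classified as iSD or iPR (depending on the sum of diameters of the target lesions), or iCR if all lesions resolve". The earlier iUPD is then labelled pseudo-progression and suspicion of progression is reset.
- **Later episodes.** If new lesions appeared at an earlier iUPD and their burden has since risen from its smallest value, resolution is blocked: "It will remain iUPD until either a decrease in the new lesion burden allows resolution to iSD or iPR".

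By contrast, PR under RECIST 1.1 (Section 10.5.1) requires "no unequivocal progression of existing non-target lesions and no appearance of new lesions".

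Table 3-1 lists ORR and DOR per iRECIST, by investigator assessment, as exploratory endpoints. SAP v3.0 Sections 5.5 and 5.5.1 defer their definitions to SAP v2.0, which was not supplied. SAP Section 5.5.2 describes only OS and PFS.

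**The concern.** Entry into iUPD depends on three kinds of lesion change. Exit from it, once nothing has worsened, depends on one. A new lesion that appears and then stays the same size meets neither the test for confirmation nor the test for persistence, so the rule sends it to resolution although nothing has resolved.

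For the endpoints this matters in two ways. A participant with a target sum at least 30% below baseline and an unchanged new lesion can become an iRECIST responder while being PD under RECIST 1.1. A participant already in response can have a progression event set aside as pseudo-progression, so that iRECIST DOR keeps running. Any excess of iRECIST ORR over RECIST 1.1 ORR would naturally be read as delayed immune response, when part of it could come from this rule.

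**Working it through.** The plan gives no figure to reproduce. The check applies the written rules to repeat scans.

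**Inputs**

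- PD on target lesions: sum at least 20% and at least 5 mm above nadir (10.5.1).
- PR: sum at least 30% below baseline (10.5.1).
- iUPD, confirmation, persistence and resolution rules (10.5.3).
- Response confirmed by a repeat scan at least 4 weeks later; scans every 6 weeks during the first 54 weeks (8.1).
- Planned denominators 26, 93 and 119 (9.2).

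**Step 1: which branch is open.** If a new lesion or non-target disease alone caused the iUPD, the target sum was not above the PD threshold on that scan. On an identical repeat scan no confirming factor is present and the sum is still not above it. Persistence fails and resolution is met.

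**Step 2: identical repeat scans, baseline sum 100 mm**

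| Trigger of iUPD | Nadir (mm) | Target sum on both scans (mm) | Repeat scan |
|---|---|---|---|
| Target sum | 80 | 100 | persistent iUPD |
| New lesion | 95 | 95 | iSD |
| New lesion | 65 | 65 | iPR |
| Non-target progression | 95 | 95 | iSD |
| Non-target progression | 65 | 65 | iPR |

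Controls at target sum 65 mm: new-lesion sum up 6 mm gives confirmed progression (iCPD), significant non-target growth gives iCPD, and new-lesion sum up 4 mm (no other factor) gives iPR. The confirmation rule therefore does stop growing lesions. What passes through is an unchanged lesion, or a measurable new one growing by less than 5 mm.

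**Step 3: a full course**

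- Baseline target sum: 80 mm.
- Week 6: 52 mm plus a new 12 mm lesion. Change = (52 − 80)/80 = −35%. The new lesion makes this RECIST 1.1 PD, hence iUPD.
- Threshold with nadir 52: the larger of 52 × 1.2 = 62.4 and 52 + 5 = 57, so 62.4 mm. If the nadir is taken as the baseline 80, it is 80 × 1.2 = 96 mm. The sum of 52 mm is below both.
- Week 12, identical: nothing worsened and the sum is not above threshold, so iPR.
- Week 18, identical: iPR again, 6 weeks later, which meets the confirmation interval.

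The participant is a confirmed iRECIST responder and is PD under RECIST 1.1.

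**Step 4: the later-episode exception.** It applies only at a subsequent iUPD and only where new-lesion burden has increased. Step 3 is a first iUPD with unchanged burden, so the exception does not reach it.

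**Step 5: size per participant.** One participant shifts ORR by 1/26 = 3.8, 1/93 = 1.1 or 1/119 = 0.8 percentage points. The documents give no frequency. If one assumes 1 to 5 such participants, the shift is 3.8 to 19.2 points at n=26, 1.1 to 5.4 at n=93 and 0.8 to 4.2 at n=119. The SAP Version History records that recruitment stopped early, so the two larger denominators may not apply.

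**The case against.** The best defence is that Section 10.5.3 is a coherent scheme: unchanged lesions do not confirm progression, earlier lesions continue to be tracked, and later growth brings iUPD back. Much of this stands, and it rules out several stronger readings.

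- *That resolution looks at nothing but the target sum.* It does not. Worsening in any lesion type leads to iCPD. The target sum decides alone only once worsening is absent, which an unchanged scan guarantees.
- *That the protocol contradicts itself.* Among the rules that apply after pseudo-progression resolves, one begins "If non-target lesions have shown previous unequivocal progression, and this progression has not resolved". That wording describes the lesions, whereas resolution there means a visit status of iSD, iPR or iCR. The protocol foresees the two coexisting and sets a lower bar for the next iUPD. That is an acknowledged consequence of the rule, and it still leaves an unchanged progression scored as iPR.
- *That every such case inflates ORR.* Only the iPR branch adds a responder. iSD does not, and a participant with a confirmed response before the iUPD counts anyway.
- *That management changes for all these participants.* In Table 10-11, clinically stable participants may continue treatment at the investigator's discretion under iUPD and under iSD/iPR/iCR alike. The repeat imaging after iUPD may coincide with the next scheduled visit. The treatment entries differ for clinically unstable participants.

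It is also fair that a fuller rule could exist elsewhere. Figure 10-1 is not shown, SAP v2.0 was not supplied, and 10.5.3 points to the iRECIST publication for further detail. None of these can be checked here. The explicit conditions in 10.5.3 would still need to be squared with any such rule.

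**Conclusion.** The point holds for the rule as written. After an iUPD triggered only by a new lesion or non-target progression, an unchanged scan must be classified iSD or iPR, and the iPR can be confirmed by a further unchanged scan. The exploratory, investigator-assessed iRECIST ORR and DOR can therefore include participants whose triggering lesion never regressed, at about 3.8 points of ORR each in a cohort of 26.

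A reader might infer that the trial's efficacy conclusion is at risk or that iRECIST ORR is materially inflated. The documents support neither. The primary endpoint is RECIST 1.1 ORR by central review, where a new lesion is PD; the expansion criterion and secondary endpoints do not use iRECIST, and PFS is defined by RECIST 1.1. No frequency is given, so the total effect on iRECIST ORR is unknown and may be nil.

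The conclusion assumes that the investigators and the derivation follow the text of 10.5.3 literally and that no fuller rule sits in the material not supplied.

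**What to change.** **Endpoint derivation.** For iRECIST ORR and DOR, count iPR after an iUPD as response only if the factor that triggered that iUPD is no longer present or has regressed: the target sum is back below threshold, new lesions are gone or decreased, or non-target disease is no longer in unequivocal progression. Where there was more than one trigger, apply this to each. Otherwise keep the visit as iUPD for the analysis. The derivation should state how large a decrease counts. At the least, the report should state the rule used and list iRECIST responders whose trigger never regressed.

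**Participant management.** The persistence, resolution and later-episode rules in 10.5.3, together with Table 10-11, must be reconciled on what resolution requires when new or non-target lesions caused the iUPD. No treatment rule is proposed here.

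**Cost.** No new scans. The analysis needs the trigger of each iUPD to be recorded or recoverable from the lesion data that sites enter in the eCRF. iRECIST ORR may be slightly lower.

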10.6 Appendix 6: CYP3A4 Inhibitors and Inducers

CYP3A4 inducers and inhibitors

Table 10–12 presents an overview of CYP3A4 inducers and **strong** CYP3A4 inhibitors. CYP3A4 inducers and **strong** CYP3A4 inhibitors are NOT allowed due to drug-drug-interaction with regorafenib.

Grapefruit juice (CYP3A4 inhibitor) should also be avoided.

Table 10-12: Overview of CYP3A4 Inducers and Strong CYP3A4 Inhibitors

Strong CYP3A4 Inhibitors	CYP3A4 Inducers
Boceprevir	Avasimibe
Clarithromycin	Bosentan
Cobicistat, only available in the combination with elvitegravir,	Carbamazepine
emtricitabine, tenofovir or disoproxil fumarate	Efavirenz
Conivaptan	Enzalutamide
Delavirdine	Etravirine
Idelalisib	Fosphenytoin
Indinavir	Hypericum perforatum (St John's
Itraconazole	Wort)
Ketoconazole	Lersivirine
Lopinavir	Lumacaftor
Mibefradil	Methylphenobarbital
Miconazole	Mitotane
Nefazodone	Modafinil
Nelfinavir	Nafcillin
Posaconazole	Phenobarbital
Ritonavir	Phenytoin
Saquinavir	Primidone
Telaprevir	Rifabutin
Telithromycin	Rifampicin
Tipranavir	Rifamycin
Troleandomycin	Semagacestat
Voriconazole	Thioridazine

CYP3A4 = cytochrome P450 3A4

Strong CYP3A4 inhibitors are NOT allowed during this clinical trial.

CYP3A4 inducers are NOT allowed during this clinical trial.

The CYP3A4 inducers and strong CYP3A4 inhibitors in Table 10–12 were identified using the Bayer-World Health Organization's Drug Dictionary (WHO-DD) and Bayer drug groupings for CYP3A4 inducers and CYP3A4 inhibitors.

Page 130 of 141

10.7 Appendix 7: New York Heart Association Functional Classification

NYHA Class	Symptoms
I	No symptoms and no limitation in ordinary physical activity, e.g. shortness of breath when walking, climbing stairs etc.
II	Mild symptoms (mild shortness of breath and/or angina) and slight limitation during ordinary activity.
III	Marked limitation in activity due to symptoms, even during less-than-ordinary activity, e.g. walking short distances (20–100 m). Comfortable only at rest.
IV	Severe limitations. Experiences symptoms even while at rest . Mostly bedbound patients.

10.8 Appendix 8: Barcelona Clinic Liver Cancer (BCLC) Classification

HCC Very early stage (0) Single ≤ 2 cm Child-Pugh A, PS 0 Early stage (A) Single, or 3 nodules ≤ 3 c Child-Pugh A–B, PS 0 Terminal stage (D) Child-Pugh C**, PS 3–4 Intermediate stage (B) Advanced stage (C) Portal invasion Multinodula Extrahepatic spread Child-Pugh A–B*, PS 1–2 Child-Pugh A-B*, PS 0 Potential candidate Single 3 nodules for liver transplantation Portal No Yes bilirubin Associated Normal Increased Yes No Ablation Resection Transplant Ablation Sorafenib Best supportive care Effective treatments with survival benefit

Figure 10-2: BCLC Staging and Treatment Strategy

HCC = hepatocellular carcinoma; MELD = model for end-stage liver disease; PS = performance status; TACE = transarterial chemoembolization Source: (Bruix et al. 2016)

The BCLC classification divides HCC patients in 5 stages (0, A, B, C and D) according to pre-established prognostic variables, and allocates therapies according to treatment-related status. Thus, it provides information on both prognostic prediction and treatment allocation. Prognosis prediction is defined by variables related to tumor status (size, number, vascular invasion, N1, M1), liver function (Child–Pugh's) and health status (ECOG). Treatment allocation incorporates treatment dependent variables, which have been shown to influence

^{*}Note that Child-Pugh classification is not sensitive to accurately identify those patients with advanced liver failure that would deserve liver transplant consideration.

^{**}Patients with end stage cirrhosis due to heavily impaired liver function (Child-Pugh C or earlier stages with predictors of poor prognosis, high MELD score) should be considered for liver transplantation. In them, HCC may become a contraindication if exceeding the enlistment criteria

Page 131 of 141

therapeutic outcome, such as bilirubin, portal hypertension or presence of symptoms-ECOG (EASL-EORTC Clinical Practice Guidelines) (EASL-EORTC 2012).

10.9 **Appendix 9: Child-Pugh Classification**

	Points Sco	red for Observe	d Findings
	1	2	3
Encephalopathy grade ^a	None	1 or 2	3 or 4
Ascites	Absent	Slight	Moderate
Serum bilirubin, mg/dL	< 2	2 to 3	> 3.0
Serum albumin, g/dL	> 3.5	2.8-3.5	< 2.8
Prothrombin time-international normalized ratio (INR)	< 1.7	1.7 - 2.3	> 2.3

Grade 0: normal consciousness, personality, neurological examination, electroencephalogram Grade 1: restless, sleep disturbed, irritable/agitated, tremor, impaired handwriting, 5 cps waves Grade 2: lethargic, time-disoriented, inappropriate, asterixis, ataxia, slow triphasic waves Grade 3: somnolent, stuporous, place-disoriented, hyperactive reflexes, rigidity, slower waves Grade 4: unrousable coma, no personality/behavior, decerebrate, slow 2-3 cps delta activity

Assessment as good operative risk (A) if 5 or 6 points; moderate risk (B) if 7 to 9 points, and poor operative risk (C) if 10 to 15 points (developed for surgical evaluation of alcoholic cirrhotics).

